9 STUDY PROCEDURES

All subjects must sign and date the IRB/Independent Ethics Committee (IEC)-approved ICF before any study-specific procedures are performed. Refer to Section 16.2.1 for further details.

9.1 Demographics

Demographic data collection will include: age, sex, race, and ethnicity and be recorded in the eCRF.

9.2 Prohibited Concomitant Medications

Investigational product with the exception of MT-1186 and intravenous edaravone are prohibited.

10 SAFETY ASSESSMENTS

10.1 Physical Examination

A full physical examination will occur at specified time points as described in Table 1 and be recorded in the eCRF. It will consist of an assessment of major body parts and systems: abdominal, cardiovascular, general appearance, head, eyes, ears/nose/throat, lymph nodes, musculoskeletal, neck, neurological, dermatological, respiratory, and 'other'.

A routine physical examination will occur at specified time points as described in Table 1 and be recorded in the eCRF. It will consist of an assessment of the following body systems: abdominal, cardiovascular, general appearance, respiratory, neurological, and other.

10.2 Vital Signs

The following measurements will be performed and be recorded in the eCRF: systolic and diastolic blood pressure, heart rate (e.g., beats per minute), respiratory rate, and axillary, oral, or tympanic body temperature (e.g., Celsius) and the same method is to be used throughout the study. Subjects must be in a supine position in a rested and calm state for at least 5 minutes before blood pressure assessments are conducted. If the subject is unable to be in the supine position, the subject should be in the most supine position as possible. The position selected for a subject should be the same that is used throughout the study and documented on the CRF.

The Investigator will perform an overall evaluation for safety purposes and the recording will be reported as 'normal', 'abnormal clinically significant (CS)', or 'abnormal not clinically significant (NCS)' and be recorded in the eCRF.

Abnormalities of clinical significance will be reported as AEs. Repeat measurements will be performed if needed.

10.3 Orthostatic Vital Sign Measurement

The following vital signs measurements will be performed and be recorded in the eCRF: systolic and diastolic blood pressure, and heart rate. Subjects must be in a seated position in a rested and calm state for at least 5 minutes before blood pressure assessments are conducted. Measure blood pressure and pulse rate. Have the patient stand. Repeat blood pressure and pulse rate measurements after standing 1 and 3 minutes. A drop in systolic blood pressure of ≥ 20 mm Hg, or in diastolic blood pressure of ≥ 10 mm Hg, or increase in heart rate >20 beats/minute or experiencing clinical orthostatic symptoms (eg lightheadedness or dizziness) is considered abnormal. If subjects cannot stand due to disease progression or other reasons, it will not be considered a protocol deviation.

The Investigator will perform an overall evaluation for safety purposes and the recording in the eCFR will be reported as 'normal', 'abnormal clinically significant

(CS)', or 'abnormal not clinically significant (NCS)'.

Abnormalities of clinical significance will be reported as AEs.

10.4 Body Weight

Body weight will be measured and recorded in kilograms in the eCRF.

10.5 12-lead Electrocardiogram

A 12-lead ECG will be performed after the subject has rested for at least 5 minutes in a supine position. The ECG must include the following measurements: R wave to R wave (RR) interval, heart rate, QRS, QT, corrected QT interval by Bazett (QTcB), and corrected QT interval by Fridericia (QTcF).

The Investigator will perform an overall evaluation of the ECG for safety purposes and the recording in the eCRF will be reported as 'normal', 'abnormal CS', or 'abnormal NCS'.

Abnormalities of clinical significance will be reported as AEs. Repeat measurements will be performed if needed.

10.6 Clinical Laboratory Tests

The following parameters will be evaluated during the study and be recorded in the eCRF (refer to Table 1 for further details).

The volume of blood and urine to be collected per time point shall be the amount necessary for measurement at each site.

10.6.1 Hematology

Red blood cell count, hemoglobin, hematocrit value, white blood cell count including differential, and platelet count.

10.6.2 Blood Chemistry

Albumin, total protein, AST, ALT, lactate dehydrogenase, alkaline phosphatase, total bilirubin, direct bilirubin, GGT, creatine kinase, total cholesterol, triglycerides, blood urea nitrogen, bicarbonate, serum glucose, serum creatinine level, uric acid, sodium, potassium, chloride, and calcium.

10.6.3 Urinalysis (Qualitative)

Protein, glucose, occult blood, urobilinogen, white blood cells, and bilirubin.

10.6.4 Pregnancy Test

For female subjects only, serum beta-human chorionic gonadotropin level will be

conducted. A serum test may be performed at the discretion of the investigator (or subinvestigator) if needed to determine pregnancy. Serum test results will be recorded in the eCRF. If the subject tests positive for pregnancy, the subject will be excluded from clinical study.

10.7 Columbia-Suicide Severity Rating Scale (C-SSRS)

The clinician will attend a certified rater training for the C-SSRS.

The C-SSRS is a clinician-rated instrument that captures the occurrence, severity, and frequency of suicide-related ideations and behaviors during the assessment period. The C-SSRS must be administered by appropriately trained site personnel. Suicidal ideation is classified on a 5-item scale: 1 (wish to be dead), 2 (nonspecific active suicidal thoughts), 3 (active suicidal ideation with any methods [not plan] without intent to act), 4 (active suicidal ideation with some intent to act, without specific plan), and 5 (active suicidal ideation with specific plan and intent). The C-SSRS also captures information about the intensity of ideation, specifically the frequency, duration, controllability, deterrents, and reasons for the most severe types of ideation. Suicidal behavior is classified on a 5-item scale: 0 (no suicidal behavior), 1 (preparatory acts or behavior), 2 (aborted attempt), 3 (interrupted attempt), and 4 (actual attempt). More than 1 classification can be selected provided they represent separate episodes. For actual attempts only, the actual or potential lethality is classified for the initial, most lethal, and most recent attempts. C-SSRS assessments are presented in Appendix 3.

11 EFFICACY ASSESSMENTS

11.1 ALS Functional Rating Scale (ALSFRS-R)

The Investigator (or subinvestigator) will evaluate ALSFRS-R as presented in Appendix 1.

ALSFRS-R (Appendix 1) is a questionnaire used to measure the impact of ALS that is evaluated by the Investigator. The scale measures the subjects' physical function across 12 activities of daily living. The date of the evaluation along with the results will be recorded in the eCRF.

11.2 Time to Death, Tracheostomy, or Permanent Assisted Mechanical Ventilation

On Day 1 of treatment with oral edaravone through EOT/ET, the Investigator (or subinvestigator) will investigate the presence or absence of the following events and record in the eCRF:

- Death
- Tracheostomy
- Permanent assisted mechanical ventilation (≥ 23 hours/day)

If any of the events are present, the onset date of the event will be recorded in the eCRF and ET assessments will be performed.

12 STUDY DRUG TREATMENT

12.1 Investigational Medicinal Product

12.1.1 Drug Product

Oral edaravone (MT-1186)

The product is a white to brown aqueous suspension of edaravone (105 mg/5 mL).

12.1.2 Formulation, Packaging, and Labeling

Oral edaravone suspension is 50 mL per bottle. The label of a bottle will contain the statement: Investigational Product: to be used in a clinical investigation only, sponsor's name and address, chemical name or code name, Lot No., and storage condition.

12.1.3 Storage Conditions

Refrigerated (2°C to 8°C)

12.1.4 Handling, Storage, and Management Methods of the Investigational Product

After concluding a study contract with the study site, the study monitor will supply the investigational product. The investigational product manager will store and manage the investigational product in accordance with the "Investigational Product Management Procedures" established by the sponsor and, after the end of the study, he/she will return all used investigational products to the monitor.

The investigational product must be used only for the purposes specified in the protocol (and must not be used for other purposes, such as other clinical studies, animal studies, or basic experiments).

12.2 Dosing of Oral Edaravone

All subjects enrolled will receive 105 mg of oral edaravone, once daily, as specified in the protocol (administered once daily for 10 days out of 14, followed by a 14-day drug-free period) in each cycle. Treatment cycles will occur every 28 days.

The dose of edaravone should be taken after an overnight fast and subjects must continue to fast at least 1 to 2 hours postdose before the next meal (eg, breakfast).

A description of the oral edaravone and study medication dispensed is provided in Table 2.

Table 2: Investigational Product

Product Name	Edaravone
Dosage Form	Oral suspension
Unit Dose	105 mg
Route	Oral/PEG/RIG tube
Physical Description	Aqueous viscous suspension
Manufacturer	Mitsubishi Tanabe Pharma Corporation

12.3 Treatment Compliance

The prescribed dosage, timing, and mode of administration of study medication may not be changed except for PEG/RIG dosing as the subject's disease progresses. Drug compliance should be assessed on a per cycle basis by site staff during their on-site study visits to assess their dosing compliance. Subjects will be asked questions regarding the compliance, and any departures from the intended regimen must be recorded in the eCRF.

Study drug accountability and treatment compliance will be documented throughout the study period.

Subjects will be asked to return all unused medication including empty and partially used medication. Study medication dispensed at the previous visit will be collected by the site and compliance will be assessed by counting the returned study medication bottles.

Non-compliance is defined as taking < 80% or > 120% of study medication during evaluation periods (visit to visit).

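### Does counting returned bottles, each holding one full cycle of doses, leave the 80% to 120% compliance definition unworkable?

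*Protocol*

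**What the plan says.** Protocol 12.1.1 gives a strength of 105 mg in 5 mL. Section 12.1.2 states "Oral edaravone suspension is 50 mL per bottle". Under 12.2 each 28-day cycle is "administered once daily for 10 days out of 14, followed by a 14-day drug-free period", which makes 10 doses.

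Section 12.3 describes compliance in several steps:

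- Timing: "Drug compliance should be assessed on a per cycle basis by site staff during their on-site study visits".
- Questioning: subjects are asked about compliance, and "any departures from the intended regimen must be recorded in the eCRF".
- Returns: "Subjects will be asked to return all unused medication including empty and partially used medication".
- Method: "compliance will be assessed by counting the returned study medication bottles".
- Definition: non-compliance is less than 80% or more than 120% of study medication from one visit to the next.

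Table 1 dispenses drug at Day 1 and Week 24. Its footnote k has staff evaluate compliance for each cycle when subjects attend.

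SAP 7.1.1.1 derives only duration of exposure and disregards non-compliance and interruptions. SAP 8.1.3 lists compliance data on the safety analysis set. SAP 7.2 records that no subject reached Week 24.

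**The concern.** The definition is a percentage with a cut at 80%, but the named method counts containers that each hold a whole cycle. A bottle that comes back part-used could have supplied anywhere from one dose to nine. If the count were the only evidence, a subject who took 11 of 20 doses and one who took 19 of 20 would look the same. No formula in either document turns the returns, or the recorded departures, into a percentage.

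This could matter because duration of exposure ignores missed doses. The compliance listing is then the planned output that shows how much drug was taken during a long-term safety study. A listing that could not separate poor from good adherence would weaken the reading of the adverse event rates.

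**Working it through.** **Inputs.** Dose volume 5 mL (Protocol 12.1.1); bottle 50 mL (12.1.2); 10 doses per 28-day cycle (12.2); cut at 80% (12.3); Week 24 as the planned second visit (Table 1). The documents state no compliance figure to reproduce. They also do not say how many bottles are dispensed or whether a part-used bottle carries over to the next cycle, so those points are assumptions.

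**Resolution.** 50 / 5 = 10 doses per bottle = 1 cycle. Day 1 to Week 24 is 24 × 7 / 28 = 6 cycles, or 60 doses.

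**Bottles emptied one after another (assumption).** Over c cycles the schedule is 10c doses and the cut is 8c. A return of e empty bottles and one part-used bottle means 10e + 1 to 10e + 9 doses taken. It is ambiguous when 10e + 1 < 8c ≤ 10e + 9.

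| Cycles | Cut (doses) | Ambiguous return | Doses taken | Percent |
|---|---|---|---|---|
| 1 | 8 | 1 part-used | 1–9 of 10 | 10–90 |
| 2 | 16 | 1 empty + 1 part-used | 11–19 of 20 | 55–95 |
| 3 | 24 | 2 empty + 1 part-used | 21–29 of 30 | 70.0–96.7 |
| 4 | 32 | 3 empty + 1 part-used | 31–39 of 40 | 77.5–97.5 |
| 5 | 40 | none | – | – |
| 6 | 48 | 4 empty + 1 part-used | 41–49 of 60 | 68.3–81.7 |

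At c cycles there are c possible returns with one part-used bottle, so 1 + 2 + 3 + 4 + 5 + 6 = 21 in all. Of these, 1 + 1 + 1 + 1 + 0 + 1 = 5 are ambiguous. At four cycles only one value, 31 doses, lies below the cut.

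**A fresh bottle each cycle (assumption).** With e empty and p part-used bottles, doses taken lie between 10e + p and 10e + 9p. Counting every mix of empty, part-used and unopened bottles, the ambiguous patterns number 1 of 3, 2 of 6, 3 of 10, 4 of 15, 4 of 21 and 7 of 28 for one to six cycles. These are counts of patterns, not probabilities.

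**The upper cut.** With exactly one bottle per completed cycle, a count cannot exceed 100%. But if six bottles (60 doses) are issued at Day 1 to reach Week 24, and the subject leaves after one to four cycles, the 120% limit is 12, 24, 36 or 48 doses. A count can then exceed it. At five cycles the limit is 60, which six bottles just reach and cannot exceed. So it cannot be said in general that the count is unable to show over-use. Protocol 13.11 also reports any greater or more frequent dose as an adverse event.

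**What the recorded departures add.** In one cycle with a part-used bottle, two recorded missed doses give 8/10 = 80%, which is not below the cut. Three give 7/10 = 70%, which is below it. Where departures are recorded as numbers of doses, they settle what the count cannot.

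**The two periods.** Footnote k to Table 1 has compliance reviewed for each cycle at the visit. The 12.3 definition applies the threshold over the interval between visits. Both can be followed together. The withdrawal criterion in 7.6 is stated in missed doses over two consecutive cycles and is not tied to the bottle count.

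**The case for a change.** The strongest case for a change is that the named method cannot, by itself, apply the definition it serves, and that the study ended where this is most visible. Because nobody reached Week 24, intervals of one to five completed cycles are the relevant ones, and the one- and two-cycle ranges are the widest. Exposure duration ignores missed doses, so a reader has only the compliance listing from which to judge intake. A stated formula, doses taken over doses scheduled, would cost little.

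The resolution point stands, as does the absence of a written formula in these two documents. The rest carries less weight. The count sits beside questioning, recorded departures and drug accountability, and Protocol 15.3.1 lists all individual subject data, so the departures will be available to read. A conversion may also sit in the sponsor's product-management procedures or eCRF entry manual, which are referred to but not included here.

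The proposed formula may not be computable from what is required. Section 12.3 asks for departures, not for a number of missed doses in each cycle, and 13.11 asks for an adverse event report, not a tally of extra doses. Writing the formula into the plan would not create those data.

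**Conclusion.** No change to the plan is called for. The bottle count is coarse: one bottle is one cycle, and some part-used returns straddle 80%. How many depends on a bottle-use rule that the documents do not state: at most one return pattern at each length if bottles are emptied in turn, and more if a new bottle is opened each cycle.

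The consequence is confined to one listing. The safety analysis set needs only one dose, exposure duration disregards compliance, there is no per-protocol set, and no test is planned. The 12.3 definition triggers no stated action, and the 80% to 120% entry criterion concerns the parent studies. This is a gap that whoever prepares the listing can fill sensibly, by reading the returns beside the recorded departures and noting in the study report how the compliance entries were obtained. That is ordinary reporting practice and needs no amendment.

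This conclusion assumes that the questioning and eCRF recording in 12.3 were carried out. If they were not, the listing would have one-cycle resolution, but still no planned summary or analysis would change.

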12.4 Subject Identification

Subjects who completed Week 96 of Study MT-1186-A03 will continue to be identified by the unique Subject Identifier that was assigned to them at the screening visit of study MT-1186-A01, and subjects who completed Week 48 of Study MT-1186-A04 will continue to be identified by the unique Subject Identifier that was assigned to them at the screening visit of study MT-1186-A02.

The Subject Identifier will be used to reference the subject during the whole duration of the study. The Subject Identifier will be documented in the subject's source documents. The Subject Identifier will be recorded on study medication labels and other documentation.

A list identifying the subjects by their unique Subject Identifier will be kept in the Investigator Site File.

12.5 Procedures for Assigning Subjects to Treatment Groups

This is an open-label study. Therefore, no randomization or blinding is applicable. This

is a single-arm study without randomization.

12.6 Dose Adjustment Criteria

Dose adjustments of oral edaravone will not be allowed.

13 ADVERSE EVENT MANAGEMENT

All AEs and SAEs will be recorded in the source documents. All AEs and SAEs that occur from the time written ICF is obtained until the end of the Safety Follow-up Period will be recorded in the eCRF. Even if an AE is assessed by the Investigator as not related to IMP, its occurrence must be recorded in the source documents and eCRF. AEs will be classified as 'treatment-emergent' if they arise following the administration of IMP or if a predose AE increases in severity following dosing.

At each study visit, after the subject has had an opportunity to spontaneously mention any problems, the Investigator should inquire about the occurrence of AEs. The questioning should be open-ended and non-leading.

13.1 Adverse Event

An AE is any untoward medical occurrence in a subject or clinical investigation subject administered a pharmaceutical product that does not necessarily have a causal relationship with this IMP. An AE can therefore be any unfavorable and unintended sign (including an abnormal laboratory finding, for example), symptom, or disease temporally associated with the use of an IMP, whether or not considered related to the IMP. Instances of aggravation of events (in terms of severity or seriousness) are treated as new AEs.

13.2 Serious Adverse Event

An SAE is defined as any untoward medical occurrence that at any dose:

- Results in death;
- Is life-threatening;
- Requires hospitalization or prolongation of existing hospitalization;
- Results in persistent or significant disability or incapacity;
- Is a congenital anomaly or birth defect;
- Is an important medical event.

Medical and scientific judgement should be exercised in deciding whether an AE is serious and whether expedited reporting is appropriate in other situations, such as important medical events that may not be immediately life-threatening or result in death or hospitalization but may jeopardize the subject or may require medical or surgical intervention to prevent one of the other outcomes listed in the above definition. These should also be considered serious.

Examples of such events are invasive or malignant cancers, intensive treatment in an emergency room or at home for allergic bronchospasm, blood dyscrasias, or convulsions that do not result in hospitalization, or development of drug dependency or

drug abuse. These should also usually be considered serious.

The term 'life-threatening' refers to an event/reaction in which the subject was at risk of death at the time of the event/reaction; it does not refer to an event/reaction, which hypothetically might have caused death if it were more severe.

Admission to a hospital as a new inpatient is deemed as meeting this criterion, even when the length of hospital stay was less than 24 hours. Transfer to other departments of the same hospital due to a newly emerged event during the hospitalization (e.g., transfer from the psychiatry ward to the internal medicine ward, from the internal medicine ward to the coronary intensive care unit, or from the neurology ward to the tuberculosis ward) is also counted as hospitalization.

SAEs will be recorded and reported as described in Section 13.7.

13.3 Severity of Adverse Events

The severity of AEs will be classified according to the following criteria:

- **Mild:** The event is transient and easily tolerated by the subject.
- **Moderate:** The event causes discomfort and interferes with the subject's general condition.
- **Severe:** The event causes considerable interference with the subject's general condition and may be incapacitating.

To ensure no confusion or misunderstanding of the difference between the terms 'serious' and 'severe', which are not synonymous, the following note of clarification is provided:

The term 'severe' is often used to describe the severity of a specific event (as in mild, moderate, or severe myocardial infarction); the event itself, however, may be of relatively minor medical significance (such as severe headache). This is not the same as 'serious', which is based on subject/event outcome or action criteria usually associated with events that pose a threat to a subject's life or functioning. Seriousness (not severity) serves as a guide for defining regulatory reporting obligations.

13.4 Relationship of Adverse Events to Investigational Medicinal Product

The causal relationship of the AE to IMP will be determined as either 'reasonable possibility' or 'no reasonable possibility' defined as:

Reasonable Possibility – The relationship of the clinical event to the IMP makes a causal relationship possible, and other drugs, therapeutic interventions, or underlying conditions do not provide a sufficient explanation for the observed event.

No Reasonable Possibility – The relationship of the clinical event to the IMP makes a causal relationship unlikely, or other drugs, therapeutic interventions or underlying

conditions provide a sufficient explanation for the observed event.

13.5 Clinical Laboratory Abnormalities and Other Abnormal Assessments

The Investigator will exercise medical judgment in deciding whether abnormal laboratory test results are clinically significant. Laboratory abnormalities, which are clinically significant, will be recorded as AEs or SAEs.

If an abnormal laboratory value or assessment is clearly related to a medically defined diagnosis or syndrome, the diagnosis or syndrome will be recorded on the AE form, not the individual laboratory values.

All 'abnormal, clinically significant' laboratory results or assessments will be followed until they resolve (return to normal or baseline values) or stabilize, or until they are judged by the Investigator to be no longer clinically significant. Repeat laboratory tests or measurements will be performed if needed.

